Our proposed research builds on a 4-year pilot intervention that developed a community-based strategy to engage male partners in the ANC services of their wives in rural Mozambique. **Homens para Saúde (HoPS) – (“Men for Health”)**, deployed respected men as community health workers and Traditional Birth Attendants (TBAs) to provide community-based counseling and accompany couples to ANC/HIV testing, and led to substantially improved service uptake within two years. In our new project, **“HoPS+”, we will implement a novel partner-based ART enrollment immediately when both partners receive simultaneous HIV diagnoses in ANC.** Our intervention will create an integrated structure to provide couple-based ART within comprehensive HIV care and treatment services. Anchored on professional and peer couples counseling, this intervention will ensure that partners are engaged and retained in care throughout pregnancy and the post-partum period.

5. Objectives

The overall goal of this project is to develop and assess the impact of a partner-based ART delivery intervention among HIV-positive expectant couples.

Our specific objectives are as follows:

Objective 1: To implement, monitor, and evaluate the impact of couple-based services on retention in care, viral suppression, and early infant diagnosis (EID) among HIV+ pregnant women and their HIV+ male partners through a cluster RCT. Implementation process variables will be collected (number of expert-couple counseling sessions, adherence to content, and evaluation of participant and peer experiences).

Objective 2: To investigate the impact of the HoPS+ intervention on hypothesized mechanisms of change.

We will determine the intervention's impact on hypothesized mechanisms of change, including (1) partner social support;^[45] (2) HIV stigma;^[46] (3) relationship empathy ^[47](4) HIV knowledge;^[48] and (5) patient trust in provider^[49] through quantitative surveys with patients at baseline and 6 months.

Objective 3: To use validated simulation models to evaluate cost-effectiveness of the HoPS+ intervention.

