Due to the potential for false positive results when many comparisons are performed, we will report test results in all abstracts, manuscripts, and presentations in a pre-determined order as ascertained by the HoPs+ investigators. For example, the order of reporting results could be male initiation, male retention, female initiation, female retention, etc.; the final order will be selected *a priori*. Because we are interested in answering multiple questions but will report all analyses in the context of the aforementioned ordering, no adjustment for multiplicity will be performed, an approach consistent with recommendations for clinical trials.[89] Analyses will be conducted using R software (www.r-project.org), and scripts will be accessible on our Vanderbilt project website.

Objective 2: Generalized linear mixed effects model will be utilized as described for Objective 1, replacing the logit transformation of the outcome with an untransformed linear outcome because the outcomes are continuous. Intervention status remains the exposure variable of interest and β_2 is the treatment effect (difference in mean levels of knowledge, stigma, etc.). As with Objective 1, gender specific models will be used to model each outcome of interest, adjusting for individual level covariates such as age, education, depression scores, and distance from clinic. Interactions between intervention status and the baseline value of each endpoint will be used to assess for modification of the intervention effect. All potential mediators found to be associated with the intervention at $p<0.20$ in Objective 2 will be included in a multi-level structural equation model (SEM) to account for clustering within clinics (Figure 2). SEM is well-suited to examining mediating and moderating processes over time [90-94]. Specification of the potential mediators as latent variables in SEM allows for better specification of measurement error, potentially reducing bias.[91, 94] Further, the capacity to detect and adjust for potential reporting bias in key study measures (e.g., does social desirability lead male partners to systematically report lower stigma) ensures that true differences in parameter estimates are not inflated by

Version 2

[figure not shown]

Figure 2: Mechanisms of Intervention Effect

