reporting bias.[95] Specific to this objective, SEM yields precise estimates of mediating and moderating relationships that adjust for the presence of all other variables in the model, more precisely capturing the complex reality of these processes. Direct (including controlled and natural), indirect (including natural), and total effects of the intervention through the mechanisms identified in Aim 2a will be estimated. Further, SEM allows for the flexible respecification and modeling of alternative mediating pathways, such as whether improved levels of social support may be associated with reduced stigma, which is in turn predictive of retention.[94] It also allows for exploring the impact of omitted variables, providing a post-hoc estimate of how robust the parameter estimates are.

Objective 3: The MTCT model is a simulation model of a cohort of pregnant women, from the time of conception through delivery. The model is a deterministic model, with a decision-tree structure, coded in TreeAgePro® software (Williamstown, MA); validation and sensitivity analyses are published.[72, 73, 96-98] Modeled events include the key steps in the EMTCT "cascade of care:" presentation to ANC; offer and acceptance of HIV testing; receipt of HIV test results; offer of, acceptance of, and adherence to ART; maternal mortality during pregnancy; HIV testing in labor for women with unknown/negative HIV status; live birth; infant HIV infection at delivery; and linkage to postnatal care and ART for mothers and infants.[99] After delivery, model outcomes for infants include vital status and HIV infection/exposure (infected, exposed-uninfected, or unexposed); model outcomes for mothers include vital status, CD4 (> or \leq 350/ μ L) and current ART receipt. These outcomes at the time of delivery are translated into long-term survival, life expectancy, and costs by simulating the lifetimes of mothers, fathers and infants in the CEPAC models.

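### The p<0.20 entry rule for the Objective 2 mediation model can leave real, pre-named mediators without an indirect-effect estimate and inflates the paths it keeps

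*Combined protocol and SAP*

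**What the plan says.** Section 5, Objective 2, fixes the candidate mechanisms in advance: "We will determine the intervention's impact on hypothesized mechanisms of change". It lists partner social support, HIV stigma, relationship empathy, HIV knowledge and trust in the provider. Section 8c assigns an instrument to each.

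Section 10 (Data Analysis, Objective 2) proceeds in two stages.

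- **Stage 1.** Each mechanism is an outcome in a mixed model with intervention status as the exposure, and "gender specific models will be used to model each outcome of interest".
- **Stage 2.** Entry to the mediation model depends on the stage 1 p-value: "All potential mediators found to be associated with the intervention at $p<0.20$ in Objective 2 will be included". That model is a multilevel SEM, so that the grouping of patients by clinic is allowed for. The text favours latent variables for the mediators: "Specification of the potential mediators as latent variables in SEM allows for better specification of measurement error".

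The estimands follow the selection: "Direct (including controlled and natural), indirect (including natural), and total effects of the intervention through the mechanisms identified in Aim 2a will be estimated".

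The section describes no split sample, second data set or post-selection correction. It gives no ICC, power or expected sample size for Objective 2. Section 7d says only that the analysis uses those enrolled participants who are alive and reachable by 6 months.

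**The concern.** A significance screen is a way of choosing among candidates. Here the choice was made in section 5, so the screen adds nothing to the definition of the question and costs something in the answer.

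An indirect effect is built from the path from intervention to mediator (a) and the path from mediator to outcome (b). The rule looks at the estimate of a and keeps the mediator only if that estimate is large relative to its standard error. The same data then supply a again in the SEM. Two things follow:

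- A real mediator with an unlucky estimate gets no indirect effect at all.
- A mediator that is kept has, on average, an a estimate that is too large, and the product a×b inherits the excess. Ordinary SEM intervals do not allow for this.

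There is also an internal tension. Section 10 values the SEM because it adjusts each mediator for the others and can trace a chain such as support acting through stigma on retention. If either link misses p<0.20, that chain cannot be fitted.

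**Working it through.** **The plan's own figure.** There is none for Objective 2. The only power statement (section 7d) concerns ART initiation: over 80% for 55% versus 71.5% with 24 clusters of 45. A two-proportion calculation needs 133 per arm for 80% power. The plan has 12 × 45 = 540 per arm, so the largest design effect allowed is 540/133 = 4.06, and the largest ICC is (4.06 − 1)/44 = 0.07. That is a different outcome, so it gives context for the ICC range below and does not supply an ICC for the scales.

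**Inputs from the documents.** Threshold p<0.20; five mediators; sex-specific screening models, hence 5 × 2 = 10 tests; 12 clinics per arm; 45 couples per clinic (section 7e says 40).

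**Assumptions, not in the documents.** Standardised effect d of 0.1, 0.2 or 0.3; ICC of 0.02, 0.05 or 0.10; no gain from matching or covariates.

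**Step 1: mediators with no effect.** Each passes with probability 0.20.

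- At least one of five passes: 1 − 0.8^5 = 67%.
- At least one of ten passes: 1 − 0.8^10 = 89%, if the tests were independent, which partners from the same couples and clinics are not.

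**Step 2: selection in standard-error units.** The two-sided cut-off is |z| > 1.2816. From the truncated normal distribution:

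| True effect / SE | Kept | Mean z if kept | Overstatement of a |
|---|---|---|---|
| 1 | 40% | 1.88 | 88% |
| 2 | 76% | 2.40 | 20% |

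**Step 3: conversion to this design.** Design effect DE = 1 + (m − 1) × ICC, and SE of a standardised difference = √(2 × DE / (12 × m)). With m = 45:

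- ICC 0.02: DE = 1.88, SE = 0.083
- ICC 0.05: DE = 3.20, SE = 0.109
- ICC 0.10: DE = 5.40, SE = 0.141

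A true effect of one SE is therefore only d ≈ 0.08 to 0.11 at ICC 0.02 to 0.05. Using a t test on 22 degrees of freedom:

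| d | Excluded (ICC 0.02 / 0.05 / 0.10) | Inflation of kept a path |
|---|---|---|
| 0.1 | 53% / 63% / 70% | 1.66 / 1.98 / 2.28 |
| 0.2 | 14% / 30% / 45% | 1.11 / 1.26 / 1.49 |
| 0.3 | 1% / 8% / 21% | 1.01 / 1.06 / 1.17 |

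The normal approximation gives 13% / 29% / 44% excluded at d = 0.2. With 40 per clinic the t-based figures at d = 0.2 are 16% / 31% / 46%. With 30 per clinic, to represent incomplete 6-month contact, they are 21% / 34% / 48%, with inflation 1.17 / 1.32 / 1.53.

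If all five mechanisms had d = 0.2 and the tests were independent, all five would enter the SEM with probability 46% / 17% / 5%.

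**Step 4: the indirect effect.** Take d = 0.2, b = 0.3 and ICC 0.05, so the true a×b is 0.060. In simulation the mean estimate is 0.060 without the screen and 0.076 among runs that pass it. For a mediator the intervention does not affect, a 5% test of the a path rejects in about 0.05/0.20 = 25% of the runs that pass.

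**Step 5: what removing the screen does to the SEM.** Count between-clinic parameters for k mediators: k + 1 means, k a-paths, one direct effect and k + 1 residual variances, or 3k + 3. Between-clinic b paths add k, and mediator covariances add k(k − 1)/2. For k = 5 this is 18 without the additions and 18 + 5 + 10 = 33 with them, against 24 clinics.

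**The case against.** **The intervention's effect on each mechanism is estimated without selection.** This stands. Objective 2 as worded in section 5 is answered by the stage 1 mixed models, which are fitted for every mechanism whatever its p-value. A reader might infer that the Objective 2 results as a whole are biased. They are not; only the follow-on mediation estimates are.

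**The harm is conditional.** This stands too. With a strong effect and a small ICC the lenient threshold does almost no damage, and the documents do not say where this trial will lie. The 88% overstatement belongs to an effect of about one standard error, which is a small effect here.

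**A null mediator that passes is merely entered in a model.** Fair. The 67% and 89% figures show how readily the screen admits noise; they are not false-positive rates for mediation.

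**Twenty-four clinics.** A reader might infer that the SEM asks more than 24 clusters can support, particularly since Appendix 2 prints 20 + 26 + 17 + 27 = 90 items before empathy. The documents do not establish that. The text does not say that single items are the indicators, or that latent variables are modelled between clinics, and the figure depicting the model was not available to this review. A random-intercept or cluster-robust SEM on scale scores could be fitted. What remains is a caution.

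**Screening keeps the SEM small, so dropping it trades one problem for another.** This is the strongest point. Deleting the rule and changing nothing else would enlarge the joint model, so the fix has to simplify the model as well.

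**Different mediators for men and women.** The screening models are sex-specific, but the text does not say that the SEM is. That the sexes would keep different mediators by chance is possible but not shown. The gap is that no rule covers a mechanism that passes in one sex only.

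**Conclusion.** The entry rule is a stated feature of the plan that works against the mediation analysis, and it is unnecessary because the five mechanisms were chosen beforehand. It can exclude real mediators, and it biases retained a paths and indirect effects away from zero. Under an assumed d of 0.2, ICC 0.02 to 0.10 and 45 per clinic, about 13-45% of real mediators are excluded and retained paths are inflated about 1.1 to 1.5 fold. At d = 0.3 and ICC 0.02 both the exclusion rate and the inflation are about 1%. These figures rest on assumed effects and ICCs, and on reading the plan as using one data set throughout, which is the natural reading since no other is described.

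This is a worthwhile, low-cost improvement to a secondary analysis. It does not touch Objective 1 or the unscreened effects on the mechanisms, and it does not show that the SEM cannot be fitted.

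**What to change.** 1. Delete the p<0.20 condition. State that the indirect effect will be reported for all five named mediators, in women and in men, whatever the mediator's p-value.
2. Make the main mediation analysis one mediator at a time, on observed scale scores, with a clinic random effect. Take intervals from resampling whole matched pairs. Each pair holds one clinic per arm (section 6), so resampling clinics inside a pair either reproduces the same two clinics or loses the contrast.
3. Keep the joint latent-variable SEM as a secondary, exploratory analysis for mutual adjustment and measurement error. State its indicators and between-clinic structure, bearing in mind that there are 24 clinics.

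The cost is SAP wording and modest programming, with no new data. The downsides are real. Ten indirect effects are always reported, and some intervals will be wide with only 12 pairs to resample. Single-mediator effects overlap and must not be summed. Measurement error is not modelled in the main version, and the chained pathways that section 10 describes move to the exploratory analysis.

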Objective 2: Individuals consented in the study will complete interviewer-assisted, quantitative study measures at baseline and by 6 months post-study enrollment, including measures of: 1) partner social support;[45] (2) HIV stigma;[46] (3) empathy [47]; (4) HIV knowledge;[48] and (5) patient trust in provider.[49]

Objective 3: Clinical outcomes of the linked models include MTCT risk at birth and weaning, pediatric life expectancy from birth, maternal and paternal life expectancy from presentation to care, and combined (maternal + paternal + pediatric) life expectancy. Economic outcomes, from the healthcare system perspective, include antenatal and postnatal program costs, lifetime maternal HIV-related healthcare costs, lifetime pediatric healthcare costs, and 1 to 5-year maternal and pediatric health care costs. We will use these outcomes to calculate incremental cost-effectiveness ratios (ICERs) in \$/life-year (LY) as the difference in combined healthcare costs (program + maternal lifetime + paternal lifetime + pediatric lifetime costs) between the two strategies, divided by the difference in combined projected life expectancy (maternal + paternal + pediatric life expectancy). For ICERs, all outcomes will be discounted at 3%/year.[79-81] We will consider a strategy to be "cost-saving" if it leads to greater combined life expectancy and lower combined costs than an alternative strategy. Following WHO guidance and evolving consensus in the field of cost-effectiveness analysis, we will consider a strategy to be "cost-effective," compared to its alternative, if its ICER is <0.5-1.0x Mozambique *per-capita* gross domestic product (GDP: \$525 in 2015)/LY. Recognizing the limitations of this approach, we will also compare ICERs to other HIV interventions in Africa, e.g., first line ART (\$500-\$5,500/LY).[82-86]

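### The SEM text assigns no baseline scale scores or demographic covariates to the paths from 6-month mediator to later retention, so the planned indirect effects may be confounded by traits the trial already measures

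*Combined protocol and SAP*

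**What the plan says.** Section 10, Data Analysis, Objective 2, describes two steps.

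- **Mixed models by sex.** These estimate the effect of arm on each scale, "adjusting for individual level covariates such as age, education, depression scores, and distance from clinic". The baseline value of each scale is used there only in an interaction with arm, to look for effect modification.
- **SEM.** Scales that pass a screen against arm at p<0.20 "will be included in a multi-level structural equation model (SEM) to account for clustering within clinics". The text adds latent mediators and an adjustment for reporting bias. It promises "Direct (including controlled and natural), indirect (including natural), and total effects of the intervention", and says that "SEM yields precise estimates of mediating and moderating relationships that adjust for the presence of all other variables in the model".

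The readable SEM text lists no covariates. It refers to Figure 2, which is not shown.

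Other sections bear on the point:

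- Section 8b: participants "will complete interviewer-assisted, quantitative study measures at baseline and by 6 months post-study enrollment", covering all five mechanism scales.
- Section 8c: PHQ-9 scores from baseline and from 6 months will serve as covariates.
- Section 10, Objective 1: every adult model will include depression scores.
- Section 7d, Objective 2: the analysis initially takes only retention after 6 months, because the 6-month scales may themselves be influenced by retention up to then.
- Section 10, end of the Objective 2 text: SEM permits a post-hoc look at omitted variables. No method or variable is named.

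**The concern.** Randomisation of clinics supports the effect of arm on each scale and the effect of arm on retention. It does not support the effect of a 6-month scale on later retention, which is an observational association within arms. A participant with high stigma or low partner support at enrolment will tend to report the same at 6 months and may also be less likely to stay in care. Unless the baseline score is in the retention equation, that stable trait can be read as an effect of the mechanism.

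Natural direct and indirect effects require that no mediator-outcome confounding is left unadjusted. The readable plan does not state this assumption and does not assign to the SEM the variables that would make it more plausible. At stake is which mechanism is credited with any gain in retention.

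**Working it through.** **Which variables are assigned where (readable text)**

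| Variable | Mixed models (arm to scale) | SEM (scale to retention) |
|---|---|---|
| Age, education, distance | Named as covariates | Not named |
| Baseline scale score | Arm interaction only | Not named |
| PHQ-9 | Named; time point not given | Possibly, through the general statements; time point not given |

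Adjustment for everything "in the model" helps only for variables that are in it.

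**Inputs.** The plan gives no sample size, power or error rate for the mediation analysis, so there is no stated figure to reproduce. From Section 7: 24 clinics with 45 couples each (24 × 45 = 1,080), or 40 each under the Sampling text (24 × 40 = 960). Objective 2 uses an unstated subset who can be contacted by 6 months. Everything below is assumed:

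- 36 people of one sex per clinic (36/45 = 80%, 36/40 = 90%), so 24 × 36 = 864.
- Trait T, standard normal. Baseline scale M0 measures T with reliability r = 1.0 or 0.8.
- 6-month scale: M6 = aX + ρT + √(1−ρ²)·e + u, with X the arm, a = 0.3 SD (or 0), ρ = 0.3 or 0.5, and clinic variance Var(u) = 0.02.
- Retention: logit P = −0.8 + 0.4X + ln(OR)·T + v, with OR = 1.0, 1.2 or 1.5 per SD and clinic ICC 0.05. M6 does not appear, so the true mediated effect is zero.

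**Analysis.** Two linear path regressions stand in for the SEM, with clinic-robust standard errors and t on 22 df, 1,000 runs per scenario. Mediation is declared when both paths have p<0.05.

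**Results with a = 0.3 (false mediation)**

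| OR per SD | ρ | Without M0 (two runs) | With M0, r = 1.0 | With M0, r = 0.8 |
|---|---|---|---|---|
| 1.0 | 0.3 | 3.7%, 4.6% | 4.9% | 3.5% |
| 1.0 | 0.5 | 5.0%, 5.2% | 5.0% | 5.0% |
| 1.2 | 0.3 | 9.0%, 9.1% | 4.4% | 5.1% |
| 1.2 | 0.5 | 17.6%, 19.8% | 3.9% | 6.6% |
| 1.5 | 0.3 | 28.3%, 33.5% | 5.3% | 6.6% |
| 1.5 | 0.5 | 64.7%, 66.9% | 5.0% | 9.8% |

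**Results with a = 0.** False mediation is at most 3.9% without M0 and 1.1% with it. It therefore needs both a real arm effect on the scale and baseline confounding. The M6-to-retention path alone, without M0, is significant in about 10% to 73% of runs for OR 1.2 to 1.5, whatever the arm effect.

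**Check by formula.** With no true effect, the unadjusted slope of retention on M6 is about ln(OR) × p(1−p) × ρ / 1.02. Retention at T = 0 is 31.0% and 40.1% in the two arms, so mean p(1−p) = (0.214 + 0.240)/2 = 0.227. The false indirect effect is 0.3 times the slope:

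- OR 1.5, ρ 0.5: 0.3 × 0.405 × 0.227 × 0.5 / 1.02 = 0.0135 (simulated 0.0130 to 0.0133).
- OR 1.2, ρ 0.3: 0.3 × 0.182 × 0.227 × 0.3 / 1.02 = 0.0036 (simulated 0.0035 to 0.0037).

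The false indirect effect is thus about 0.4 to 1.3 percentage points of retention. It is small in absolute terms, yet often enough to be declared significant.

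**The case against.** **The text is incomplete, not exclusionary.** A reader might infer that the SEM contains no baseline variable at all. The documents do not support that. Figure 2 cannot be read, and the statements on depression scores in Section 8c and under Objective 1 can be taken to cover every adult model. The SEM is also said to estimate moderation, so baseline scores could enter that way. This stands. But the moderation described concerns the effect of arm on each scale, and a baseline score that enters only the mediator equation does not close its route to retention. The PHQ-9 statements also leave open use of the 6-month score, which is post-randomisation and cannot serve as a baseline confounder.

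**Safeguards exist.** Restricting to retention after 6 months secures temporal order, but a trait present at enrolment precedes both variables. Latent variables and the reporting-bias adjustment address measurement. The omitted-variable check is relevant but unspecified and post hoc, and does not replace adjustment for variables already collected.

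**The size is assumed.** This stands in full. No trait effect, correlation or arm shift comes from the documents, and two regressions are simpler than a multilevel latent-variable SEM. A reader might also infer that the mediator paths are certainly confounded, or always biased away from zero. Neither follows: presence, direction and size depend on unknown trait effects.

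**The SEM is a follow-on analysis.** Section 5 and Study Question 2 define Objective 2 chiefly as the effect of the intervention on the mechanisms, which randomisation protects. This stands and limits the consequence.

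**Conclusion.** The concern holds in a conditional form. As far as the text can be read, the SEM's paths from mediator to retention are given no baseline scale score, age, education or distance, and the PHQ-9 time point is left open. If stable baseline traits affect both the 6-month scale and later retention, and the arm shifts the scale, the indirect effects may be biased and an inert mechanism may be credited. Under the assumed inputs, false mediation is about 9% to 67% without the baseline score and about 4% to 10% with it. Both analyses give about 4% to 5% if there is no confounding, and the rate is at most about 4% if the arm does not move the scale. The true size in this trial is unknown. The randomised arm comparisons in Objectives 1 and 2 are not affected.

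**What to change.** In Section 10, Objective 2:

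1. Enter the following in both the mediator equations and the retention equation of the SEM: the baseline score of each included mediator scale, baseline (not 6-month) PHQ-9, age, education and distance from clinic, plus prior ANC and parity for women.
2. State that direct and indirect effects assume no further mediator-outcome confounding. Name retention up to 6 months as one such source, since Section 7d recognises that it may influence the 6-month scales and baseline adjustment does not remove it.
3. Turn the post-hoc omitted-variable check into a pre-specified sensitivity analysis, with its method and range stated.

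**Cost.** No new data: the scales and PHQ-9 are collected at baseline, and the other variables are already planned covariates. The model becomes larger. If all five mediators enter, there are 5 + 1 = 6 equations and 5 + 4 = 9 covariates, so 9 × 6 = 54 added person-level paths, or 11 × 6 = 66 for women, before any measurement model for the baseline scales and with only 24 clinics. Imperfect scales leave some bias (up to about 10% false mediation in the check at reliability 0.8), which is why the sensitivity analysis is still needed.
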